## 4.2.2 Primary Endpoint (Normokalemia)

*Occurrence (yes/no) of normokalaemia (NK) ( $K^+$  between 3.5 and 5.0 mmol/L, inclusive) at 180 days post-discharge*

### 4.2.2.1 Definition

Primary estimand definition:

- Population: Full analysis set
- Endpoint: Occurrence (yes/no) of NK at 180 days post-discharge
- Intercurrent event strategy: Participants who discontinue treatment with a  $K^+$  measurement at 180 days post-discharge will have this value used irrespective of treatment discontinuation (treatment policy strategy). Use of rescue therapy for HK will be considered to be non-response (composite variable strategy). RAASI down-titration (including discontinuation) will be considered to be non-response (composite variable strategy). Participants who die of any cause prior to 180 days post-discharge, or who are lost to follow-up for any reason will be considered to be non-response (composite variable strategy).
- Population level summary (analysis): Logistic regression analysis with response (occurrence) as the dependent variable and randomised treatment group (reference level SoC) and participant recruitment country as the independent variables. The odds ratio along with the two-sided 95% confidence intervals and two-sided p-value (significance declared  $< 0.05$ ) will be displayed.

### 4.2.2.2 Derivations

NK will be a binary variable, derived as a  $K^+$  value between 3.5 and 5.0 mmol/L, inclusive classified as yes and  $K^+$  value  $< 3.5$  or  $K^+$  value  $> 5.0$  mmol/L classified as no.

### 4.2.2.3 Handling of Dropouts and Missing Data

Participants who die prior to 180 days post-discharge, who are missing an assessment at visit 10 or who are lost to follow-up for any reason will be considered to be non-response for the primary analysis.

### 4.2.2.4 Primary Analysis of Primary Endpoint

Occurrence (yes/no) will be compared between treatment groups in the FAS using a logistic regression model including response as the dependent variable and randomised treatment (reference level SoC) and participant recruitment country as an independent variable, and

will be tested using a two-sided alpha = 0.05. For participants who are assigned a non-response value, a sub table will be provided to summarize the intercurrent events, which led to this assignment, by treatment group. The common odds ratio will be derived together with the two-sided 95% confidence interval.

#### 4.2.2.5 Sensitivity Analyses of the Primary Endpoint

The analyses of the primary endpoint will be repeated as per section 4.2.2.4 but with alternative modelling:

- Population level summary (analysis): Providing there are sufficient participants within each covariate to support the analysis, the logistic regression model will include randomised treatment group and the following baseline variables: age (as a cubic spline), sex (male/female), participant recruitment country, presence of heart failure (yes/no), diabetes (yes/no), RAASi use (yes/no), CKD stage and baseline  $K^+$  ( $5.0 < K^+ \leq 5.5$  versus  $5.5 < K^+ \leq 6.5$  mmol/L) as independent variables. Sufficient participants for a covariate to be included will be considered if there are more than 10 participants with an event in each level of the covariate.

The analyses of the primary endpoint will be repeated as per section 4.2.2.4 but the estimand will be varied:

- Intercurrent event strategy: As primary estimand, but participants needing rescue therapy for HK will follow the treatment policy strategy (i.e., regardless of the intercurrent event).
- Intercurrent event strategy: As primary estimand, participants with RAASi down-titration (including discontinuation) will follow the treatment policy strategy (e.g. regardless of the intercurrent event).
- Intercurrent event strategy: As primary estimand, but participants who die or are lost to follow-up prior to 180 days post-discharge will not be evaluated (completers analysis only).
- Hypothetical strategy: As primary estimand, but participants who are lost to follow-up after 90 days (visit 7) or who are missing  $K^+$  status at 180 days will have their  $K^+$  status at 90 days, if available, carried forward to 180 days and included in the analysis using the principle of last observation carried forward.
- COVID-19 supplementary analysis: Intercurrent events not related to COVID-19 will be treated as per section 4.2.2.4. Participants who discontinue treatment due to COVID-19 will be treated as missing (hypothetical strategy). Use of rescue therapy for HK due to COVID-19 will be considered to be non-response (composite variable strategy). RAASi down-titration due to COVID-19 (including discontinuation) will be considered to be non-response (composite variable strategy). Participants who die due to COVID-19 will be treated as missing (hypothetical strategy).

- Alternative population: As primary estimand, but the per protocol set (PPS) will be used as the population for analysis. Payer relevant sensitivity analysis: An alternative definition of normokalaemia will be applied where NK will be a binary variable, derived as a  $K^+$  value between 3.5 and 5.5 mmol/L, inclusive classified as yes and  $K^+$  value  $< 3.5$  or  $K^+$  value  $> 5.5$  mmol/L classified as no. Analysis will be conducted as per section 4.2.2.4.
- No visit windowing: As primary estimand but all  $K^+$  measurements recorded in EDC as a visit 10 study visit while the participant remains on SZC will be used in analysis. No visit windowing (Section 3.3.2) will be applied.

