^a Any time study drug dose is adjusted, or if in either treatment arm, a concomitant medication which may affect K⁺ levels is changed (eg, use of RAASi or diuretics), the participant needs to return to the site 7 (\pm 2) days later for a K⁺ measurement and recording of adverse events and concomitant medications.

Participants randomised to Arm B will be discharged without SZC and will receive SoC per local practice for managing their K⁺ until the EOT (180 days post-discharge). The SoC will be at the discretion of the treating physician; however, participants intended to be discharged with a K-binder will not be randomised. However, participants in Arm B may have a K-binder prescribed at Day 7 post-discharge (or after Day 7 post-discharge) to treat confirmed HK or in case there is an increase in K⁺ level since discharge that, in the investigator's opinion, requires therapy.

The K⁺ levels will be measured at on-site visits at Days 7 (local laboratory), 90 (local and central laboratories), and 180 (local and central laboratories) (see Sections 8.1.1 and 8.2.4). Overall monitoring frequency will depend upon a variety of factors including other medications, progression of CKD, and dietary K⁺ intake. It is the responsibility of the treating physicians to check the participant K⁺ as medically appropriate/in accordance with the label (for both SZC and SoC arms). In addition to the scheduled on-site visits, participants should return to the site for a local K⁺ measurement 7 (\pm 2) days after any dose adjustment to SZC.

Additionally, participants in either treatment arm should have their K⁺ measured locally 7 (\pm 2) days after changes are made to medications that affect K⁺ levels (eg, use of RAASI or diuretics).

Such additional K⁺ checks and site visits will take place as clinically indicated and the resulting data, including AEs and concomitant medication information, relating to these visits will also be collected during the study.

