7 DISCONTINUATION OF STUDY INTERVENTION AND PARTICIPANT DISCONTINUATION/WITHDRAWAL

7.1 Discontinuation of Study Intervention

7.1.1 Permanent Discontinuation of Study Intervention

It may be necessary for a participant to permanently discontinue (definitive discontinuation) study intervention. If study intervention is permanently discontinued, the participant will be followed up according to the SoA ([Table 1](#)). See the SoA for data to be collected at the time of discontinuation of study intervention and follow-up for any further evaluations that need to be completed.

To minimize risk for events related to severe hypokalaemia, the following discontinuation criterion will be followed:

- Confirmed $K^+ < 3.0$ mmol/L by taking a second measurement after a ≥ 10 -minute interval, at any time during the study, the participant should immediately receive appropriate medical intervention and study intervention should be permanently discontinued.

To minimize risk for events related to severe HK, the following discontinuation criterion will be followed:

- Confirmed $K^+ > 6.0$ mmol/L by taking a second measurement after a ≥ 10 -minute interval, at any time during the study, the participant should immediately receive appropriate medical intervention and study intervention should be permanently discontinued.

To minimize risk for events related to prolongation of QT interval corrected (QTc), the following discontinuation criteria will be followed:

- If an absolute QTc > 550 ms, or an increase in QTc interval > 60 ms from baseline to more than 500 ms is reached, the participant should immediately receive appropriate medical intervention and be permanently discontinued from the study intervention. The QTcF algorithm is recommended. All participants meeting the QTc > 500 ms criterion should immediately have K^+ assessed, if not already done within 1 hour of performing the electrocardiogram (ECG).

For serious arrhythmia (eg, associated with $K^+ < 3.5$ or > 5.6 mmol/L), study drug should be permanently discontinued.

Other reasons for discontinuation of study intervention may include:

- Participant decision; the participant is at any time free to discontinue treatment, without prejudice to further treatment.
- Incorrectly randomised participant, in whom the inclusion/exclusion criteria violation would put the participant at undue risk. This will require a discussion with the medical team, who will provide a final outcome / action.

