## AMENDMENT HISTORY

CATEGORY Change refers to:	Date	Description of change	In line with CSP?	Rationale
Primary or secondary endpoints	15-Jan-2025	Additional sensitivity analysis from primary endpoint to analyse all K+ measurements recorded in Electronic Data Capture (EDC) at visit 10 while on SXC irrespective of visit windowing.	No	To explore the sensitivity of the results to the use of visit windowing.
Primary or secondary endpoints	15-Jan-2025	ECG results from site 7001 are excluded from analysis.	No	A serious breach was identified at this site with the recording of ECG measurements. To avoid bias these measurements are excluded.
Analysis Populations	15-Jan-2025	The per protocol set definition was updated to exclude important protocol deviations considered to have a major effect on efficacy.	No	Previous definition was too broad and did not reflect the purpose of the analysis population, which is to be used for sensitivity analyses of efficacy endpoints.

CATEGORY Change refers to:	Date	Description of change	In line with CSP?	Rationale
Primary or secondary endpoints	27-Nov-2023	In the definition of the first secondary objective and endpoint, “time to first occurrence of hospital admissions or ED visits with HK as a contributing factor”. In relation to this change, a sensitivity analysis with hospital admission with HK as a contributing factor has been added as well as 2 secondary objectives and endpoints.	Yes, version 4.	To expand the definition of the main secondary endpoint to encompass a wider range of hospital admissions to facilitate a larger, clinically meaningful effect size for detection in order to reduce sample size.
Other: Sample size	27-Nov-2023	The sample size was re-calculated based on the new definition of the secondary endpoint.	Yes, version 4.	To align with changes in the main secondary endpoint.
Other: Interim analysis	27-Nov-2023	The planned interim analysis has been cancelled.	Yes, version 4.	Due to the decreased sample size, running an interim analysis is not justified.

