### **3.3.2 Visit Window**

For all populations, assessments will be assigned to visits and analysis periods for categorical summaries as follows:

- Assessments with missing data and assessments marked “Not Done” will be considered as providing a missing response and are not permitted to be assigned to a visit window.
- The worst value (e.g. out of reference range preferred to within range; abnormal preferred to normal) will be used in each window. If multiple assessments fall within the same window with equal value, then the first non-missing value will be used for the summary.
- In the AZ Standard TFL shells, “Time Point” is used interchangeably with “Visit” as, in this study; multiple observations are not made at the same visit.

Target day and protocol/analysis visit windows in Table 2 and Table 3 are with respect to the date of randomisation. Visit windowing related to the date of hospital admissions and ED visits will use Table 2. All other assessments will use visit windowing provided by Table 3. Alternative windowing is required because outpatient phase visits 5, 6, 8 and 9 are conducted by phone and collect information on concomitant medication, adverse events, hospital admission and ED visits only. Target day and protocol analysis visit windows in Table 4 are with respect to the date of last dose of SZC (EOT).

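### The 'no visit windowing' check of the primary endpoint also restricts K+ to values taken on SZC, so it cannot isolate the effect of windowing

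*SAP*

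**What the plan says.** - **The check.** The last bullet of SAP 4.2.2.5 keeps the primary estimand but uses K+ "measurements recorded in EDC as a visit 10 study visit while the participant remains on SZC will be used in analysis". It adds: "No visit windowing (Section 3.3.2) will be applied".
- **Its purpose.** The SAP Amendment History (15 January 2025) gives one reason: "To explore the sensitivity of the results to the use of visit windowing". The same row repeats the on-drug restriction.
- **The primary estimand.** Under SAP 4.2.2.1, participants who stop treatment and have a K+ "measurement at 180 days post-discharge will have this value used irrespective of treatment discontinuation (treatment policy strategy").
- **Follow-up after stopping.** Protocol 7.1.1: "If study intervention is permanently discontinued, the participant will be followed up according to the SoA". A Visit 10 K+ is therefore planned for them.
- **The comparator.** Protocol 6.2: "Participants randomised to Arm B will be discharged without SZC and will receive SoC per local practice". The footnote to Protocol 6.7.1 counts SZC added later in Arm B as rescue, which is non-response in the primary.
- **Missing values.** SAP 4.2.2.3: participants "who are missing an assessment at visit 10 or who are lost to follow-up for any reason will be considered to be non-response", a rule stated for the primary analysis.
- **Choosing among values.** SAP 3.3.2: "The worst value (e.g. out of reference range preferred to within range; abnormal preferred to normal) will be used in each window". SAP Table 3 sets the Visit 10 analysis window for K+ at Days 136-186. SAP 4.2.2.2 gives no selection rule of its own.

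**The concern.** A check on windowing should change the windowing and nothing else. This one also replaces treatment policy with an on-drug condition that has no counterpart in the SoC arm. If its result differs from the primary, the reader cannot tell whether the day window or the on-drug restriction is responsible. If it agrees, the two changes may have offset each other.

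The question deserves a clean answer: the K+ analysis window for Visit 10 is 51 days wide (136 to 186), against 13 days (174 to 186) in the protocol window, and this is the only analysis added to test it.

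A smaller matter follows from the same bullet. By switching off Section 3.3.2 it implies that 3.3.2 otherwise governs the primary. The only selection rule there is the worst value, so another central K+ in the window could displace the Day-180 value that the estimand names.

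**Working it through.** **Inputs.** NK rates 0.88 (SZC) and 0.59 (SoC), and 20% drop-out after randomisation: Protocol 9.2.1. About 130 randomised, so 65 per arm: Protocol 4.1. The share off drug at Visit 10, their NK rate and the timing of stopping are not in the documents; the values below are assumptions.

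**1. The plan's own figure.** Pooled two-sided chi-square at 5%, power 80%, mean rate 0.735: n = [1.960 × √(2 × 0.735 × 0.265) + 0.842 × √(0.88 × 0.12 + 0.59 × 0.41)]² / 0.29² = 35.2, so 36 per arm, as stated. Enrolment is 72/0.8/0.8 = 112.5, so 113. Neither figure is in dispute.

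**2. Baseline.** With drop-outs as non-responders: 0.8 × 0.88 = 0.704 and 0.8 × 0.59 = 0.472, difference 0.232.

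**3. Literal reading.** Arm B is not on SZC, so it has essentially no eligible values. If those participants count as non-responders, SoC response is about 0; if they are excluded, there is no comparator. With equal true rates of 0.59 and no drop-out, the first version would show 38/65 against 0/65.

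**4. Condition applied to Arm A only.** Let d be the share of Arm A participants with a Visit 10 K+ who are off drug, and q their NK rate. On-drug responders are 0.8 × (0.88 − q × d). If off-drug participants become non-responders, that is the Arm A rate. If they are excluded, divide by 1 − 0.8 × d. Arm B stays at 0.472.

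| d | q | Arm A, non-response | Difference | Arm A, excluded | Difference |
|---|---|---|---|---|---|
| 5% | 0.59 | 0.680 | 0.208 | 0.709 | 0.237 |
| 10% | 0.59 | 0.657 | 0.185 | 0.714 | 0.242 |
| 20% | 0.59 | 0.610 | 0.138 | 0.726 | 0.254 |
| 5% | 0.88 | 0.669 | 0.197 | 0.697 | 0.225 |
| 10% | 0.88 | 0.634 | 0.162 | 0.689 | 0.217 |
| 20% | 0.88 | 0.563 | 0.091 | 0.670 | 0.198 |

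No window was altered in any row. The whole movement from 0.232 comes from the SZC condition, and it can go either way.

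**5. The worst-value note.** Protocol 8.1.1 has central K+ taken at discharge, Day 90, Day 180 and the early-discontinuation (E/D) visit. A second central value in the Visit 10 window is therefore mainly an E/D sample in Days 136-179 (44 days) or a repeat. If stopping is spread evenly over 180 days, the share of Arm A with both an E/D and a Visit 10 K+ in the window is 0.8 × d × 44/180, which is 1.0% at d = 5% and 3.9% at d = 20% (0.6 to 2.5 of 65). As an upper bound, let every such E/D value be abnormal and the Visit 10 NK rate be 0.59. The loss is then 0.006 to 0.023, and the difference falls from 0.232 to between 0.226 and 0.209.

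**The case against.** **On the check.** The bullet stands in a list introduced as varying the estimand, and the amendment row discloses the restriction. The clause may also have a purpose. Without windows there is no Day-186 limit, and Arm A stops study drug after the outpatient phase, so a late Visit 10 could be off drug simply because the regimen had ended. The literal reading makes a two-arm model meaningless and is unlikely to be programmed. It also borrows the missing-data rule of 4.2.2.3, which is written for the primary analysis.

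Part of this stands. The literal reading shows that the wording is defective; it does not predict the output. Carrying 4.2.2.3 into the check is an inference from its being defined as the primary estimand. The rest does not rescue the check. The intercurrent-event bullets beside it name the strategy that they change; this one names none and gives windowing as its only reason. A screen for late values that works through SZC use acts on one arm only, and it also discards planned Visit 10 values from participants who stopped early.

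**On the worst-value rule.** Section 3.3.2 is worded for categorical summaries. The safety sections (SAP 4.6.3.2, 4.6.6.2, 4.6.7.2) send multiple results to it expressly, and SAP 4.2.2 does not. The estimand text points to one Day-180 value. Some E/D cases could not change status in any event: under Protocol Table 4, K+ above 6.0 leads to rescue, which is already non-response. This largely stands, and it reduces the matter to a clarification.

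**Conclusion.** The main point holds on the text alone, without any assumed rate: the check alters the handling of treatment discontinuation along with the windowing, so a difference from the primary cannot be attributed to windowing. Under the Arm A reading, the assumed 5-20% off drug moves the difference from 0.232 to between 0.091 and 0.254, depending on the off-drug NK rate and on a handling rule that the SAP leaves open. These figures show the room for ambiguity; they are not forecasts. They take the planning rates at face value and do not model rescue or RAASi down-titration.

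A reader might infer three stronger things that the documents do not support:

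- **That the primary result is at risk.** The analysis is supportive and leaves the primary unchanged.
- **That the SAP makes the worst value the primary endpoint value.** This is an inference from the exemption in 4.2.2.5. Under the assumptions above it concerns at most about 1 to 3 of 65 in Arm A.
- **That local or unscheduled K+ could enter the primary.** Protocol 8.1.1 and 8.2.4 reserve central K+ for endpoints and the main analyses, and SAP Section 2 lists no change to that.

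**What to change.** **SAP 4.2.2.5**, one of two options:

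- Delete the on-SZC condition. Use the central-laboratory K+ recorded as Visit 10 in both arms, whatever its study day, with every other intercurrent-event rule as in the primary.
- Keep the present version under a separate on-treatment label, and state how SoC participants and off-drug Arm A participants are handled. The windowing question then still needs its own check.

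**SAP 4.2.2.2**, a short clarification:

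- The primary uses the central Visit 10 K+ falling in the Day 136-186 analysis window. The window must stay in the definition, or the no-windowing check has nothing to test.
- E/D, unscheduled and follow-up values do not replace it. Say also whether such a value can count when there is no Visit 10 sample; 4.2.2.3 as it stands points to non-response.
- Name the value to take if a central Visit 10 sample is repeated, and use the same rule in the check.
- The worst-value rule of 3.3.2 does not apply to the primary endpoint.

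The cost is SAP wording and a small programming change. No extra data or visits are needed.

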#### 4.2.2.6 Subgroup Analyses

Subgroup analyses will be performed using separate logistic regression models, as per section 4.2.2.4, by age (18-64, 65-84 and  $\geq 85$  years), sex (female, male), recruitment country (France, Italy, Spain, UK, Belgium and Netherlands), presence of heart failure (Yes/No, identified per Medical History using an SMQ of “Cardiac Failure”; SMQ Code: 20000004), diabetes (Yes/No, identified per Medical History eCRF using a PT of “Type 2 diabetes mellitus”), RAASI use at screening (Yes/No, identified per Concomitant Medication eCRF as CMCLASCD in (‘C09AA’, ‘C09BA’, ‘C09BB’, ‘C09BX’, ‘C09CA’, ‘C09DA’, ‘C09DB’, ‘C09DX’, ‘C09XA’) where Start Date is prior to date of informed consent), CKD stage, without diagnosis of CKD (but eGFR  $< 90$  ml/min/1.73m^2), baseline  $K^+$  ( $5.0 < K^+ \leq 5.5$  versus  $5.5 < K^+ \leq 6.5$  mmol/L) at baseline, an alternative baseline  $K^+$  categorisation ( $5.0 < K^+ \leq 5.5$ ,  $5.5 < K^+ \leq 6.0$ , and  $6.0 < K^+ \leq 6.5$  mmol/L) and by duration of index hospitalisation ( $< 7$  days versus  $\geq 7$  days). Subgroup analyses will only be conducted providing there are 10 or more events per subgroup category.

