5 STUDY POPULATION

Prospective approval of protocol deviations to recruitment and enrolment criteria, also known as protocol waivers or exemptions, is not permitted. Rescreening of participants is allowed as detailed in Section [5.4](#).

The distribution of participants across the range of K^+ levels will be operationally controlled by ensuring that the following ratios are met:

- Approximately 50% enrolled participants with mild HK (K^+ between > 5.0 and ≤ 5.5 mmol/L) and approximately 50% with moderate/severe HK (K^+ between > 5.5 and ≤ 6.5 mmol/L)
- A minimum of 30% of enrolled participants in each group.

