1.1 Synopsis 3 Objectives and Endpoints 9.1 Statistical Hypothesis 9.4.3.2 Secondary Endpoints	Secondary objective #3 is edited and is now focusing on number of hospitalisation preceding enrolments or ED visits, both with HK as a contributing factor.	To be more relevant to clinical decision making
1.1 Synopsis 3 Objectives and Endpoints 9.1 Statistical Hypothesis 9.4.3.2 Secondary Endpoints	A new secondary objective is added to evaluate effect of sodium zirconium cyclosilicate (SZC) on reducing the risk of RAASi down-titration.	Though undesirable, RAASi down-titration is a treatment option for managing HK: recent guidelines describe reducing RAASi as a last resort
1.1 Synopsis 3 Objectives and Endpoints 9.1 Statistical Hypothesis 9.4.3.2 Secondary Endpoints 9.4.3.3 Exploratory Endpoints	Secondary objectives #4 to #10 are moved to exploratory objectives.	To simplify the secondary endpoints

Section # and Name	Description of Change	Brief Rationale
1.1 Synopsis 1.2 Schema 1.3 Schedule of Activities 4.2 Scientific Rationale for Study Design 5.1 Inclusion Criteria 6.1 Screening and Inpatient Phase	Inclusion criterion #4: Definition of HK for eligibility is modified. Clarifications are also provided for sources of these potassium (K ⁺) values.	To better describe the appropriate and addressable population
1.1 Synopsis 1.2 Schema 4.1 Overall Design 5 Study Population 9.4.3.1 Primary Endpoints 9.4.3.2 Secondary Endpoints 9.4.3.3 Exploratory Endpoints	The study now plans to enrol approximately equal numbers of participants with mild HK (K ⁺ between > 5.0 and ≤ 5.5 mmol/L) and with moderate/severe HK (K ⁺ between > 5.5 and ≤ 6.5 mmol/L), with a minimum of 30% of the enrolled participants in either group. As a consequence, K ⁺ levels were adjusted in sensitivity analyses sections for primary, secondary, and exploratory endpoints.	To describe the benefit seen for mild HK versus moderate/severe HK with SZC post-discharge
1.1 Synopsis 4.1 Overall Design 4.2 Scientific Rationale for Study Design 5.2 Exclusion Criteria 6.1 Screening and Inpatient Phases	It is clarified that participants treated by a K-binder at the current ED visit/hospital admission can be enrolled in the study under certain conditions.	Clarification edit

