#### **4.2.3.7 Subgroup Analyses**

Subgroup analyses will be performed using separate Cox models, as per section 4.2.3.4, by age (18-64, 65-84 and over 85 years), sex (female, male), recruitment country (France,

Italy, Spain, UK, Belgium and Netherlands), presence of heart failure (Yes/No, identified per Medical History using an SMQ of “Cardiac Failure”; SMQ Code: 20000004), diabetes (Yes/No, identified per Medical History eCRF using a PT of “Type 2 diabetes mellitus”), RAASI use at screening (Yes/No, identified per Concomitant Medication eCRF as CMCLASCD in (‘C09AA’, ‘C09BA’, ‘C09BB’, ‘C09BX’, ‘C09CA’, ‘C09DA’, ‘C09DB’, ‘C09DX’, ‘C09XA’) where Start Date is prior to date of informed consent), CKD stage, without diagnosis of CKD (but eGFR  $<90 \text{ ml/min/1.73m}^2$ ), baseline  $K^+$  ( $5.0 < K^+ \leq 5.5$  versus  $5.5 < K^+ \leq 6.5 \text{ mmol/L}$ ), an alternative baseline  $K^+$  categorisation ( $5.0 < K^+ \leq 5.5$ ,  $5.5 < K^+ \leq 6.0$ , and  $6.0 < K^+ \leq 6.5 \text{ mmol/L}$ ) and by duration of index hospitalisation ( $<7$  days versus  $\geq 7$  days hospitalisation during the inpatient phase). Subgroup analyses will only be conducted providing there are 10 or more events per subgroup category.

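### No treatment-by-subgroup interaction is planned, so the mild versus moderate/severe hyperkalaemia comparison behind the K+ quota has no estimate of its own

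*SAP*

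**What the plan says.** SAP 4.2.2.6 (primary endpoint): "Subgroup analyses will be performed using separate logistic regression models, as per section 4.2.2.4". Section 4.2.2.4 models response on treatment and recruitment country. Its comparison "will be tested using a two-sided alpha = 0.05", and its output is described thus: "The common odds ratio will be derived together with the two-sided 95% confidence interval".

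SAP 4.2.3.7 (main secondary endpoint): "Subgroup analyses will be performed using separate Cox models, as per section 4.2.3.4". Sections 4.2.4.7 to 4.2.8.7 repeat the pattern with Cox or negative binomial models.

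A subgroup is analysed only "providing there are 10 or more events per subgroup category". For the primary endpoint, SAP 4.2.2.6 does not say whether an event is a response or a non-response.

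Protocol section 5 sets the enrolment mix: "Approximately 50% enrolled participants with mild HK", a similar share with moderate/severe HK, and at least 30% in each group. Protocol Appendix D gives the Amendment 2 reason for this quota: "To describe the benefit seen for mild HK versus moderate/severe HK with SZC post-discharge".

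The only interaction terms in either document are treatment by time, in the K+ and eGFR mixed models. In the covariate-adjusted sensitivity models (for example SAP 4.2.2.5), baseline K+ enters as a main effect only.

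**The concern.** Mild versus moderate/severe is a contrast between strata. Separate models give an effect, a CI and a p-value within each stratum, but nothing on the difference between strata. K+ severity is not an incidental subgroup, because the protocol shapes enrolment around it.

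The risk lies in interpretation. When each stratum has only moderate power, two strata with the same true effect will often fall on opposite sides of 0.05 by chance. With no interaction estimate beside them, such a pair of results is easily read as benefit in one severity group and none in the other. The primary test and the testing hierarchy are not affected.

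**Working it through.** **Inputs.** Protocol 9.2.1: response 0.88 (SZC) and 0.59 (SoC), two-sided 5%, 80% power. Protocol 9.2.2: HR 0.329, event proportions 17% and 43.2%, 20% drop-out after randomisation. Protocol 4.1: 130 randomised (65 per arm), 104 evaluable. SAP 4.2.2.3: a missing Visit 10 assessment or loss to follow-up counts as non-response.

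**The plan's own figures.**
- Primary, with mean response 0.735: n = [1.96√(2×0.735×0.265) + 0.8416√(0.88×0.12 + 0.59×0.41)]² / 0.29² = 35.2, so 36 per arm, as stated.
- Main secondary: ln 0.83 / ln 0.568 = 0.329. Freedman's formula gives 31 events; 31/0.301 = 103, so 52 per arm, as stated.

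**Assumptions for the stratum check.** The true effect is identical in both K+ strata, all 130 randomised fall in one of the two, and country is ignored. Drop-outs counted as non-responders are spread evenly, so 0.88×0.8 = 0.704 and 0.59×0.8 = 0.472.

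**Primary endpoint.** Stratum power is Φ{[√n·d − 1.96√(2p̄q̄)] / √(p₁q₁ + p₂q₂)}, where n is the number per arm in the stratum, d the difference in response rates, p̄ the mean rate and q = 1 − p. The probability that exactly one stratum is significant is P₁(1−P₂) + P₂(1−P₁).

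| Rates | Split (n per arm) | Power in each stratum | Exactly one p<0.05: formula | Simulated |
|---|---|---|---|---|
| 0.88 / 0.59 | 50/50 (32.5, 32.5) | 0.767, 0.767 | 0.357 | 0.335 |
| 0.88 / 0.59 | 30/70 (19.5, 45.5) | 0.539, 0.893 | 0.470 | 0.439 |
| 0.704 / 0.472 | 50/50 (32.5, 32.5) | 0.475, 0.475 | 0.499 | 0.502 |
| 0.704 / 0.472 | 30/70 (19.5, 45.5) | 0.308, 0.617 | 0.545 | 0.542 |

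The simulations used 200,000 trials per row, whole-number strata (33 and 32, or 20 and 45, per arm) and likelihood-ratio tests. In the same trials a Wald interaction test at 5% falsely signalled a difference in 3.1%, 3.0%, 4.6% and 4.4% respectively.

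**Main secondary endpoint.**
- The 104 evaluable give 104×0.301 = 31.3 events, or 15.65 per half.
- Power per half: Φ(√15.65×0.671/1.329 − 1.96) = 0.515. Exactly one half significant: 2×0.515×0.485 = 0.50.
- If all 130 were followed in full: 130×0.301/2 = 19.6 events per half, power Φ(√19.6×0.671/1.329 − 1.96) = 0.61, and 2×0.61×0.39 = 0.48. The choice of denominator matters little.

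**Precision of the interaction, primary, 50/50.**
- SE of the difference in log odds ratios at 0.88/0.59: √{2×[1/(32.5×0.1056) + 1/(32.5×0.2419)]} = 0.915. The 95% CI spans a factor of exp(1.96×0.915) = 6.0 each way.
- 80% power needs a ratio of odds ratios near exp(2.80×0.915) ≈ 13.
- If the odds ratio is 5.1 in one stratum and 1 in the other, power is 51% (41% at 30/70 with the effect in the smaller stratum).
- At 0.704/0.472 the SE is 0.736 and the factor is 4.2.

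**Strata may be smaller.** Protocol 5.1 (criterion 4) admits participants already normokalaemic under treatment. SAP 3.3.1.1 takes the last value before the first SZC dose as baseline, and the K+ categories in SAP 4.2.2.6 start above 5.0. These participants fit neither category.

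**The event gate.** Expected responders are 65×(0.704 + 0.472) ≈ 76 of 130, leaving about 54 non-responders. If an event means a response, the gate counts the commoner class. It also counts per category, not per arm. With 10 SZC participants in a category, the chance of no SZC non-responder is 0.88¹⁰ = 28% (0.704¹⁰ = 3% with drop-outs), and the odds ratio is then not estimable.

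**The case against.** A reader might infer that the plan answers the severity question by comparing two p-values. The documents do not support that. The SAP sets no comparison rule, the parent analyses give odds or hazard ratios with 95% CIs, and subgroups are outside the testing order in SAP Table 5. The 36% to 54% figures therefore describe what happens if readers dichotomise at 0.05. The plan does not commit itself to doing so.

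A reader might also infer that a trial objective goes unmet. Protocol section 3 has no objective on effect by severity. The purpose appears only in the amendment rationale and is to describe, which stratum estimates with CIs do in part.

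Two further readings go too far. That the gate counts responders is an inference, because the term is left undefined; ten responders with no non-responders at all would be an extreme case when about 54 non-responders are expected. That fitting country inside each level adds material noise has not been calculated.

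Finally, an interaction test here has low power. That stands, but it favours reporting the ratio: a wide CI shows that an apparent difference is uninformative, which separate stratum results do not show directly.

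**Conclusion.** The point holds as a gap in exploratory reporting. No between-stratum estimate or test is planned for any subgroup, including the one that the enrolment quota was set up to describe, so the comparison stays informal.

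Under equal true effects, a split verdict on the primary endpoint would arise by chance in about 36% (50/50, protocol rates) to about 54% (30/70, drop-outs as non-response) of trials, and in about 50% for the main secondary endpoint. These figures rest on the assumptions listed with the calculation. The quota applies to enrolled participants, so the split among those randomised may differ. Normokalaemic participants would shrink the strata further. The design sample sizes are not in dispute.

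**What to change.** For each subgroup factor, fit one model in the FAS with treatment, factor, treatment × factor and the main-analysis covariates, with country not entered twice when it is the factor. Report level-specific effects and the ratio of effects (odds, hazard or rate ratios) with 95% CIs, and the interaction p-value. Name K+ severity as the key factor, label everything exploratory, and make no within-level significance claims. State how participants normokalaemic at baseline are classified.

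For the primary endpoint, apply the count of 10 to the smaller of responders and non-responders in each level, and require at least one of each in each arm before an odds ratio is reported.

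The cost is SAP wording, with no new data or visits. The downside is imprecision: the ratio's 95% CI will span about a factor of 6 each way, so a non-significant interaction must not be read as evidence of equal effects.
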